7.6. Pharmacokinetic Analyses

[figure not shown]
[figure not shown]
The PK calculations will be performed, if appropriate, using commercial software such as WinNonlin® (Pharsight Corporation, Mountain View, CA). Nominal times will be used in all cases, except when the difference between the actual time and nominal time is greater than 5 minutes for samples collected up to 4 hours after administration; in these cases, actual time will be used for PK analysis.

The PK parameters of C_{max} , t_{max} , C_{min} , and AUC_{0-t} (INCAGN01949) will be summarized by part, dose, and study cycle. The log-transformed PK parameters will be compared among dose levels by using a 1-factor analysis of variance. Dose-dependent parameters (C_{max} and AUC) will be normalized to the lowest common dose before statistical comparisons. Additionally, if sufficient data are available, the dose proportionality of INCAGN01949 C_{max} and AUC will be evaluated statistically by using a power model (eg, $AUC = \alpha \cdot (dose)^\beta$) or equivalently $\log(AUC) = \log(\alpha) + \beta \cdot \log(dose)$, where linear dose proportionality is accepted if β is not significantly different from 1).

If there is a sufficient amount of plasma concentration data from this study, then the data will be analyzed by standard population PK methods using appropriate software (eg, NONMEM). The effect of covariates on PK parameters will be evaluated. The covariates will include, but not be

limited to, demographics (age, weight, sex, race), clinical laboratory test values, and concomitant medications.

The relationship between plasma concentrations of INCAGN01949 and the baseline-subtracted change in QTc interval will be explored graphically and analyzed using a linear mixed-effect model.

8. SAFETY AND TOLERABILITY

Sample data displays are provided in [Appendix A](#).

8.1. General Considerations

Summary tables may be replaced with listings when appropriate. For instance, an AE frequency table may be replaced with a listing if it only contains a few unique PTs reported on relatively few subjects. Data from the Part 1 portion will be summarized separately where appropriate. Additional summaries for specific subgroups may be included on an ad hoc basis.

Unless otherwise stated, table summaries will be limited to AEs occurring within 60 days of the last administration of study drug.

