5.4.7. Definition, Procedures, and Supportive Care Guidelines for Immune-Related Adverse Events

INCAGN01949 is an immune modulator, and although no toxicities were identified in preclinical models, it is possible that irAEs (both nonserious and serious) similar to those described with approved immunotherapies may occur. Adverse events of a potential immunologic etiology or irAEs may be defined as an AE consistent with an immune phenomenon associated with drug exposure *after all other etiologies have been eliminated* (see [Section 8.8](#)). Immune-related AEs may be expected based on the nature of INCAGN01949, its mechanism of action, and reported experience with other immunotherapies. Special attention should be paid to AEs that may be suggestive of potential irAEs. An irAE can occur shortly after the first dose or several months after the last dose of treatment. Suspected irAEs should be discussed with the medical monitor when possible.

Subjects should receive appropriate supportive care measures as deemed necessary by the treating investigator. Suggested supportive care measures for the management of drug-related AEs with potential immunologic etiology are outlined in [Table 5](#). Detailed supportive care guidelines for specific irAEs can be found in [Appendix B](#). For each AE, attempts should be made to rule out other causes including, but not limited to, metastatic disease or bacterial or viral infection, which might require specific supportive care.

Table 5: Supportive Care Guidelines for Subjects Exhibiting Immune-Related Adverse Events

CTCAE Grade/Severity	Supportive Care ^a
Grade 1 (mild)	
 • Monitor symptoms and provide symptomatic treatment.
Grade 2 (moderate)	
 • Monitor symptoms and provide symptomatic treatment. • Consider consultation with specialists as necessary. • Consider systemic corticosteroids per institutional standard of care.

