6.4. Follow-Up

6.4.1. Safety Follow-Up

The safety follow-up period is the interval between the EOT visit and the scheduled follow-up visit, which should occur 30 days (+ 7 days) and 60 days (+ 7 days) after the EOT visit (or after the last dose of study drug if the EOT visit was not performed). Adverse events and SAEs must be reported up until at least 60 days after the last dose of study drug, the date of the follow-up visit, or until toxicities resolve, return to baseline, or are deemed irreversible, whichever is longer. If a subject is scheduled to begin a new anticancer therapy before the end of the 30-day or the 60-day safety follow-up period, then the safety follow-up visit should be performed before new anticancer therapy is started.

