8.1.2. Reporting

Adverse events that begin or worsen after informed consent should be recorded on the Adverse Events form of the eCRF. Conditions that were already present at the time of informed consent should be recorded on the Medical History form in the eCRF. Monitoring for the occurrence of new AEs should be continued for at least 60 days after the last dose of study drug or until the start of new anticancer therapy, whichever occurs first. Adverse events (including laboratory abnormalities that constitute AEs) should be described using a diagnosis whenever possible rather than by individual underlying signs and symptoms.

The term "disease progression" should be recorded as an AE/SAE only if there are no other identifiable AEs/SAEs associated with the disease progression at the time of reporting. For events associated with disease progression, the relevant signs and symptoms should be reported using a diagnosis whenever possible rather than individual underlying signs and symptoms. When a clear diagnosis cannot be identified, each sign or symptom should be reported as a separate AE. If the events resulting from disease progression meet the criteria for an SAE (eg, resulted in hospitalization, a life-threatening event, or death), the specific event(s) should be reported as an SAE(s) as described in [Section 8.3.2](#). In both cases (ie, AEs or SAEs related to disease progression), it should be indicated that each event (reported as a diagnosis or as signs and symptoms) is related to disease progression on the Adverse Events form of the eCRF.

The severity of AEs will be assessed using CTCAE v4.03 Grades 1 through 4. The CTCAE v4.03 severity of Grade 5 will not be used; AEs resulting in death will be graded accordingly using Grades 1 through 4 and have the outcome noted as fatal. If an event is not classified by CTCAE, the severity of the AE will be graded according to the scale below to estimate the grade of severity:

Grade 1	Mild; asymptomatic or mild symptoms; clinical or diagnostic observations only; intervention not indicated.
Grade 2	Moderate; minimal, local, or noninvasive intervention indicated; limiting age-appropriate activities of daily living.
Grade 3	Severe or medically significant but not immediately life-threatening; hospitalization or prolongation of hospitalization indicated; disabling; limiting self-care activities of daily living.
Grade 4	Life-threatening consequences; urgent intervention indicated.

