8.3.2. Reporting

Every SAE, regardless of suspected causality (eg, relationship to study drug(s) or study procedure or disease progression), occurring after the subject has signed the ICF through the last study visit (or 60 days after the last dose of study drug, whichever is later) must be reported to the sponsor (or designee) within **24 hours** of learning of its occurrence, unless otherwise specified by the Protocol. Any SAEs occurring more than 60 days after the last dose of study drug should be reported to the sponsor or its designee only if the investigator suspects a causal relationship to the study drug.

Information about all SAEs is collected and recorded on the Adverse Event form of the eCRF. The investigator must assess and record the causal relationship of each SAE to the study treatment.

The investigator must also complete the Incyte Serious Adverse Event Report Form, in English, and send the completed and signed form to the sponsor or designee within 24 hours of becoming aware of the SAE. The investigator must provide a causality assessment, that is, assess whether there is at least a reasonable possibility that the SAE is related to the study treatment: suspected (yes) or not suspected (no). Refer to the Incyte Reference Guide for Completing the Serious Adverse Event Report Form.

The contact information of the sponsor's study-specific representatives is listed in the investigator manual provided to each site. The original copy of the SAE Report Form and the confirmation sheet must be kept at the study site.

Investigational site personnel must report any new information regarding the SAE within 24 hours of becoming aware of the information in the same manner that the initial SAE Report Form was sent. Follow-up information is recorded on an amended or new SAE Report Form, with an indication that it is follow-up to the previously reported SAE and the date of the original report. The follow-up report should include information that was not provided on the previous SAE Report Form, such as the outcome of the event (eg, resolved or ongoing), treatment provided, action taken with study drug because of the SAE (eg, dose reduced, interrupted, or discontinued), or subject disposition (eg, continued or withdrew from study participation). Each recurrence, complication, or progression of the original event should be reported as follow-up to that event, regardless of when it occurs.

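### SAP 8.1 cuts the AE tables at 60 days after last dose with no exception, so related SAEs collected later appear only in listings

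*SAP*

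**What the plan says.** SAP 8.1 gives a default for all AE tables: "Unless otherwise stated, table summaries will be limited to AEs occurring within 60 days of the last administration of study drug". SAP 8.2.1 defines a treatment-emergent AE (TEAE) as one that is new or worse after the first dose, with no end date, as does Protocol 9.4.2.1. It also keeps every AE in the data listings, whatever its timing.

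The Protocol says of irAEs, in the same words in 5.4.7 and 8.8: "An irAE can occur shortly after the first dose or several months after the last dose of treatment".

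On collection, the Protocol says:

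- 8.1.2, new AEs: "Monitoring for the occurrence of new AEs should be continued for at least 60 days after the last dose of study drug", or until new anticancer therapy starts if that is sooner.
- 6.4.1, AEs and SAEs: "Adverse events and SAEs must be reported up until at least 60 days after the last dose of study drug", extended to the follow-up visit or to resolution of toxicities if longer. The safety visits are those "which should occur 30 days (+ 7 days) and 60 days (+ 7 days) after the EOT visit".
- 8.3.2, SAEs of any causality: until the later of the last study visit and 60 days after last dose. An SAE beyond 60 days still has to go to the sponsor, but "only if the investigator suspects a causal relationship to the study drug". No end date is given.

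**The concern.** The primary endpoint is the frequency, duration and severity of AEs. The Protocol singles out irAEs as a class that can be delayed by months and keeps collecting suspected-related SAEs accordingly. The SAP default then leaves those late reports out of every count and percentage. Because SAEs reported long after the last dose are those suspected to be drug-related, the omission can only make the tabulated safety profile look more favourable.

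The tables would also not reveal the limit. The AE shells footnote the open-ended TEAE definition, and none mentions 60 days, so a reader would take the related-SAE, fatal-event and irAE tables as complete.

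**Working it through.** The check compares the table window with the collection windows. "Day" below counts from the last dose, and I read the SAP's wording as referring to the date of onset, which it does not define.

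**Step 1: is an exception stated?** The default yields wherever the SAP says otherwise. SAP 8.2.1 to 8.2.5 contain no such statement. Nor do the Appendix A titles and shells for fatal events (3.2.11), SAEs (3.2.12, 3.2.13), related SAEs (3.2.15) or irAEs (3.2.19 to 3.2.22). The cut applies to all of them.

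**Step 2: what is collected after Day 60?**

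| Event | Collected until | Tabulated until |
|---|---|---|
| SAE suspected related | no limit (Protocol 8.3.2) | Day 60 |
| AE or SAE up to a later safety visit | that visit (Protocol 6.4.1), subject to the new-therapy stop in 8.1.2 | Day 60 |
| Non-serious irAE starting well after follow-up | mostly not required | not applicable |

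A related serious or fatal event at Day 90 is thus reported and listed but not tabulated.

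**Step 3: how late can the second safety visit fall?** The Protocol gives two anchors.

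- From the last dose (Table 7, footnote b): 60 + 7 = Day 67, which is 67 − 60 = 7 days past the cut.
- From the EOT visit (6.4.1): the interval from last dose to EOT is not given. Assume 14 to 28 days (one scheduled cycle, up to the 28-day delay limit in Protocol 5.4.9), plus the 3-day EOT window in Table 7. The latest visit is then 14 + 3 + 67 = Day 84, or 28 + 3 + 67 = Day 98. These are 84 − 60 = 24 and 98 − 60 = 38 days past the cut.

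**Step 4: weight of one omitted subject.** 1/6 = 16.7 percentage points in a full escalation cohort, 1/9 = 11.1 in a 9-subject cohort and 1/17 = 5.9 in a full Part 2 cohort. This is a scale only, not an estimate of how many subjects would be affected.

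**The case against.** The best defence is that 60 days is the Protocol's own minimum monitoring period. Up to then new AEs are sought systematically; long after it, only SAEs that the investigator suspects are related need be reported. Restricting rates to the period of systematic ascertainment is sound, and mixing selectively reported late events into the same percentages would not be. This stands. It is a reason to keep the main window and not to pool, but not a reason to leave late related events out of the tables altogether.

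Second, nothing is lost. Appendix A plans listings of SAEs, fatal AEs, deaths, related AEs and irAEs, and SAP 8.2.4 says the number of subjects with irAEs will be listed by dose level and tumor type. This also stands, but a listing is not an incidence table, and 8.2.4 covers irAEs only. SAP 8.2.5 also plans a Kaplan-Meier analysis of Grade 3 or higher related irAEs. It states no censoring rule, and Appendix A has no table or figure for it, so it cannot be relied on to show late events.

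Third, SAP 8.1 and 8.2.5 allow a sparse table (10 or fewer subjects) to become a listing, so some affected tables may never be produced. That is optional; where the table is produced, the cut applies.

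Fourth, no dosing decision rests on these tables. Under Protocol 5.4.2 the MTD uses events to study Day 28, and later toxicities may lower it. Protocol 4.1.2 and SAP 3.1.3 let Part 2 decisions consider AEs whenever they occur. This stands and limits the priority.

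**Conclusion.** The point holds in a limited form. As written, the SAP leaves two groups of collected events out of every incidence table: treatment-related SAEs starting after Day 60 (including serious irAEs and fatal related events), and AEs between Day 60 and a later follow-up visit. The conclusion rests on the texts alone. Only the Day 84 to 98 range needs an assumption, and the related-SAE gap does not depend on it.

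Three stronger readings are tempting, and the documents do not support them:

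- A reader might infer that late irAEs in general are collected and then dropped. Non-serious irAEs starting well after follow-up are mostly not collected, so no table rule could recover them.
- A reader might infer that a large share of irAEs goes missing. The documents give neither an onset distribution nor the fraction of irAEs that start after the last dose, so no magnitude is claimed.
- A reader might infer that dose selection or safety oversight is compromised. Those decisions are not confined to the 60-day tables.

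This is a reporting gap in the primary-endpoint tables, of low-to-moderate priority, with no bearing on dose or clinical management.

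**What to change.** Keep 60 days as the main window for the general TEAE tables and state it in their footnotes beside the TEAE definition.

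Add to SAP 8.1 that treatment-related SAEs, fatal related AEs and collected irAEs are also tabulated whatever their onset. Put onset after 60 days in a separate row, not pooled with the within-window rate, and flag events that start after new anticancer therapy. Separation matters most in the fatal and SAE tables, where the within-window figures cover any causality and the late events are largely those suspected to be related.

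The cost is one or two SAP sentences, a footnote, and an added row in the related-SAE, fatal-event and irAE shells. No new data are needed. The downside is that the late events come from selective reporting, so the row is a count and should be labelled as such, not read as a complete incidence rate.

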8.2. Adverse Events

8.2.1. Adverse Event Definitions

A TEAE is any AE either reported for the first time or worsening of a pre-existing event after first dose of study drug. Analysis of AEs (as discussed below) will be limited to TEAEs, but data listings will include all AEs regardless of their timing in relation to study drug administration.

Adverse events will be tabulated by MedDRA PT and SOC. Severity of AEs will be graded using the NCI CTCAE. The CTCAE version 4.03 is used for this study. The CTCAE reporting guidelines and grading details are available on the Cancer Therapy Evaluation Program website.

The subset of AEs considered by the investigator to be related to study drug will be considered to be treatment-related AEs. If the investigator does not specify the relationship of the AE to study drug, the AE will be considered to be treatment-related. The incidence of AEs and treatment-related AEs will be tabulated. In addition, SAEs will also be tabulated.

A grading (severity) scale is provided for each AE term. If the toxicity is not included in the CTCAE v4.03 criteria, it will be rated on a scale of 1 to 4 as follows: 1 = mild, 2 = moderate, 3 = severe, and 4 = life threatening. All toxicities will be graded based on the worst level reached, not the level they may have reached if they had not been treated. When the intensity of an AE changes over time for a reporting period (eg, between visits), each change in intensity will be collected as an AE until the event resolves. Only the worst grade will be reported in AE summaries. Also, the Grade 3 or higher AEs will be reported in a listing.

Any missing onset date, causality, or severity must be queried for resolution. Unresolved missing causality and severity will be handled according to the following rules:

- An unresolved missing causality will be considered treatment-related.
- An unresolved missing severity will be identified as an unknown severity.

For purposes of analysis, all AEs will be considered TEAEs unless the AE can unequivocally be defined as not treatment-emergent.

8.2.2. Dose-Limiting Toxicities

The number of subjects with DLTs and the type of DLT will be listed by dose level. If a dose with multiple schedules is tested, the DLTs will be summarized by dose and by schedules.

8.2.3. Maximum Tolerated Dose

- In Part 1 of the study, the MTD will be defined as 1 dose level below that at which \geq one-third of subjects in a particular cohort have DLTs.
- In Part 2 of the study, toxicities will continue to be monitored. If the cumulative incidence of DLTs occurs in \geq 33% of subjects after 6 subjects have been observed for at least 28 days, further enrollment may be interrupted, and the investigators and sponsor will meet and reassess the MTD. All AEs, regardless of the time of occurrence on study, may be considered in DLT determination purposes.

8.2.4. Immune-Related Adverse Events

The number of subjects with irAEs and type of irAE will be listed by dose level (and by schedules) and by tumor type. Adverse event terms will be reviewed periodically without respect to treatment group by the medical monitor and clinical scientist to determine which AE terms correspond to irAEs. This periodic review may also occur after database lock. The medical monitor and clinical scientist will also review investigator reported AEs to determine if they qualify as irAEs. For example, a rash will be counted as an irAE even if the investigator did not report it as an irAE.

8.2.5. Adverse Event Summaries

An overall summary of AEs by treatment group and by tumor type as applicable will include the following:

- Number (%) of subjects reporting any TEAEs
- Number (%) of subjects reporting any DLTs
- Number (%) of subjects reporting any SAEs
- Number (%) of subjects reporting any Grade 3 or higher TEAEs
- Number (%) of subjects reporting any TEAEs related to INCAGN01949
- Number (%) of subjects who dose interrupted INCAGN01949 because of TEAEs
- Number (%) of subjects who permanently discontinued INCAGN01949 because of TEAEs
- Number (%) of subjects with INCAGN01949 dose reductions because of TEAEs
- Number (%) of subjects who had a fatal TEAE
- Number (%) of subjects who withdrew from study because of an TEAE

The following summaries will be produced by MedDRA term (if 10 or fewer subjects appear in a table, a listing may be appropriate):

- Summary of TEAEs by SOC and PT
- Summary of TEAEs by PT in decreasing order of frequency
- Summary of TEAEs by SOC, PT, and highest CTCAE grade/maximum severity
- Summary of Grade 3 or higher TEAEs by SOC and PT
- Summary of INCAGN01949 treatment-related AEs by SOC and PT
- Summary of Grade 3 or higher INCAGN01949 treatment-related AEs by SOC and PT
- Summary of all TEAEs, treatment-related AEs, Grade 3 or 4 TEAEs, and treatment-related Grade 3 or 4 TEAEs.
- Summary of INCAGN01949 treatment-related AEs by SOC, PT, and highest CTCAE grade/maximum severity

- Summary of TEAEs leading to death by SOC and PT
- Summary of treatment-emergent SAEs by SOC and PT
- Summary of treatment-emergent SAEs by PT in descending order of frequency
- Summary of INCAGN01949 treatment-related SAEs by SOC and PT
- Summary of TEAEs leading to INCAGN01949 dose reduction by SOC and PT
- Summary of TEAEs leading to INCAGN01949 dose interruption by SOC and PT
- Summary of TEAEs leading to discontinuation of INCAGN01949 by SOC and PT
- Summary of treatment-emergent non-SAE by SOC and PT.
- Summary of irAEs by SOC and PT.
- Summary of Grade 3 or higher irAEs by SOC and PT.
- Number (%) of subjects reporting an immune-related AE (irAE)
- Number (%) of subjects reporting any Grade 3 or 4 irAE
- Number (%) of subjects reporting an immune-related treatment-related AE (irAE)
- Number (%) of subjects reporting an immune-related treatment-related Grade 3 or 4 AE (irAE)

A KM analysis of time to first TEAE of Grade 3 or higher will be conducted. A KM analysis of time to first treatment-related irAE of Grade 3 or higher will be conducted.

8.3. Clinical Laboratory Tests

8.3.1. Laboratory Value Definitions

Laboratory values and change from baseline values will be summarized descriptively by visit. Baseline will be determined according to [Section 4.1.3](#). If there are multiple values that meet the criteria for baseline, additional rules may be provided after consultation with the medical monitor to delineate which value will be defined as baseline.

Laboratory test values outside the normal range will be assessed for severity based on CTCAE grade or similar criteria where clinical intervention is required for CTCAE grading. The incidence of abnormal laboratory values and shift tables relative to baseline will be tabulated.

